10.4.4 Multiplicity Consideration

To control for inflation of type 1 error rate due to multiple hypotheses, the analysis of the two primary endpoints will be conducted in a hierarchical manner.

If both primary endpoints demonstrate statistically significant superiority of NOV03 versus saline at the two-sided alpha = 0.05 level, the following secondary endpoints will be tested hierarchically to maintain an overall two-sided alpha = 0.05.

1. CFB of Dryness Score (VAS) at Day 15
2. CFB in total Corneal Fluorescein Staining (tCFS) (NEI scale) at Day 15
3. CFB of VAS burning/stinging at Day 57
4. CFB in central Corneal Fluorescein Staining (cCFS) (NEI scale) at Day 57

10.4.5 Primary Efficacy Analyses

The primary comparisons in this trial will be between NOV03 versus saline at Day 57 in the FAS with available data per subject using the following estimands:

- Population: Subjects with DED defined through enrollment criteria
- Endpoint:
 - CFB in tCFS in the study eye at Day 57
 - CFB of Dryness Score (VAS) at Day 57
- Intercurrent event:
 - Discontinuation of study medications is ignored. [treatment policy strategy]
 - Non-optimal compliance is ignored. [treatment policy strategy]

- Withdrawal due to any reason. Missing data not imputed. [hypothetical strategy]
- Population-level summary:
 - Difference in the mean CFB in tCFS in the study eye at Day 57 between NOV03 and saline.
 - Difference in the mean CFB of Dryness Score (VAS) at Day 57 between NOV03 and saline.

If the overall study discontinuation rate is $\geq 5\%$ then the primary analysis will be based on imputation methodology using the following estimands and the available data analyses will become robustness analyses.:

- Population: Subjects with DED defined through enrollment criteria
- Endpoint:
 - CFB in tCFS in the study eye at Day 57
 - CFB of Dryness Score (VAS) at Day 57
- Intercurrent event:
 - Discontinuation of study medications is ignored. [treatment policy strategy]
 - Non-optimal compliance is ignored. [treatment policy strategy]
 - Withdrawal due to lack of efficacy or adverse events. Baseline observation carried forward (BOCF) is used to impute missing data [hypothetical strategy].
 - Missing data without withdrawal or withdrawal due to reasons other than lack of efficacy or adverse events. Multiple imputations using randomized treatment-based Markov Chain Monte Carlo is used to impute missing data [hypothetical strategy].
- Population-level summary:
 - Difference in the mean CFB in tCFS in the study eye at Day 57 between NOV03 and saline.
 - Difference in the mean CFB in Dryness Score (VAS) at Day 57 between NOV03 and saline.

The primary comparison in this trial will be between NOV03 versus saline at Day 57. The primary efficacy endpoints (e.g. CFB in total corneal fluorescein staining [NEI scale] and Dryness Score) will be tested using hierarchical fixed sequence testing and summarized descriptively (n, mean, standard deviation, median, min, and max) and analyzed separately using an ANCOVA model with terms for baseline value, and treatment.

Least squares mean for each treatment group and for the difference between treatment groups will be presented from each model together with two-sided p-values (used for primary inference) and 95% confidence intervals.

Two-sample t-tests, Wilcoxon rank sum tests and mixed-effect repeated measures analysis comparing treatment groups will be performed as sensitivity analyses. The mixed-effect repeated measures model will include treatment, baseline value, visit, and the interaction between treatment and visit as fixed effects, and subject as a random effect. An unstructured

covariance matrix will initially be used to model the covariance among repeated measures; however, if the model fails to converge using this covariance structure, either heterogeneous TOEPLITZ, homogeneous TOEPLITZ, or compound symmetry will be implemented according to the Akaike information criterion with a correction for finite sample sizes (AICc).

10.4.6 Secondary Efficacy Analyses

The following secondary endpoints will be tested hierarchically:

1. CFB of Dryness Score (VAS) at Day 15.
2. CFB in tCFS (NEI scale) at Day 15.
3. CFB VAS burning/stinging at Day 57.
4. CFB in central Corneal Fluorescein Staining (cCFS) (NEI scale) at Day 57.

Inference will only be made on these endpoints, at a 2-sided alpha = 0.05, if both primary endpoints and any higher order secondary endpoints are statistically significant at a 2-sided alpha = 0.05 in favor of NOV03.

Quantitative secondary efficacy endpoints will be summarized similarly to the primary efficacy endpoints.

The primary analysis of the secondary endpoints will use the FAS with available data per subject, assuming the overall study discontinuation rate is <5%. If the overall study discontinuation rate is $\geq 5\%$, then the primary analysis of the secondary endpoints will be based on imputation methodology as defined in [Section 10.4.5](#) and the available data analyses will become robustness analyses.

10.4.7 Other Pre-specified Efficacy Analyses

The analyses of other pre-specified endpoints will use the Full Analysis Set (FAS) with available data per subject.

1. CFB of Dryness Score (VAS) at Day 29.
2. CFB in tCFS at Day 29.
3. CFB in CFS central and inferior sub-regions (NEI scale) to each measured post-baseline visit.
4. Proportion of tCFS responders (≥ 3 improvement based on NEI scale) at Day 57.
5. Proportion of Dryness Score responders ($\geq 30\%$ improvement from baseline) at Day 57.
6. CFB in VAS burning/stinging, sticky feeling, foreign body sensation, itching, blurred vision, sensitivity to light, pain, frequency of dryness, and awareness of dry eye symptoms at each measured post-baseline visit.
7. CFB in Ocular Surface Disease Index (OSDI[®]) at each measured post-baseline visit.

Quantitative other pre-specified efficacy endpoints will be summarized descriptively (n, mean, standard deviation, median, min and max) by visit, and analyzed similarly to the primary endpoint at each measured visit. Least squares mean for each treatment group and

for the difference between treatment groups will be presented from the model together with two-sided p-values and 95% confidence intervals.

Two-sample t-tests, Wilcoxon rank sum tests and mixed-effect repeated measures analysis will also be presented as sensitivity analyses.

Other pre-specified endpoints evaluating the proportion of study eyes (or subjects) meeting pre-defined criteria will be presented and tested between treatment groups using logistic regression analysis adjusting for baseline tCFS score at each measured follow-up visit. Pearson chi-squared analysis comparing the treatment groups will be performed as sensitivity analyses.

Exploratory and other endpoints will be summarized and analyzed similarly to the other pre-specified endpoints.

10.4.10 Safety Variables Analyses

All safety analyses will be performed on the Safety Population. The primary evaluation of safety of the active arm will be against the control arm.

Extent of Exposure

Dosing information for each treatment and each subject will be listed. Discontinuation of treatment will be summarized by treatment received. The primary reason for IMP discontinuation will also be summarized by treatment received.

Analysis of Adverse Events

Adverse events (AEs) will be coded using the MedDRA dictionary. Frequencies and percentages of subjects with TEAEs, serious TEAEs, and TEAEs causing premature discontinuation will be provided by treatment group. An AE is treatment emergent if it occurs or worsens after the first dose of trial treatment. Furthermore, frequencies will be

given of subjects with TEAEs by system organ class; by system organ class and preferred term; by system organ class, preferred term and maximal severity; by system organ class, preferred term and strongest relationship; and by system organ class, preferred term, maximal severity, and strongest relationship. Separate summaries will be performed for ocular and non-ocular AEs.

The treatment groups will be compared in regard to safety endpoints descriptively. No inferential comparison will be conducted.

Concomitant Medications

Concomitant medications will be coded using the most recent version of WHO-Drug Dictionary and summarized by treatment group.

Other safety endpoints including those assessed by visual acuity, slit-lamp biomicroscopy, dilated fundoscopy, and intraocular pressure will be summarized by treatment group and visit using descriptive statistics. Changes from baseline will also be summarized where appropriate. For assessments performed by eye, study eye and fellow eye will be summarized separately.

10.4.11 Interim Analyses

No interim analyses are planned for this trial.

10.5 Additional Analyses

No further analysis is planned.

10.6 Methods to Minimize Bias

This is a randomized treatment assignment, double-masked, multi-center trial. Subjects will be instructed not to show or discuss the properties of the assigned Investigational Medicinal Product (IMP) and/or their experience with the IMP with other trial participants, and not to show or discuss the IMP with the Investigator or site staff other than the dedicated dosing coordinator, unless instructed to do so.

A dedicated dosing coordinator at each site will be responsible for instructing subjects regarding IMP handling/administration, IMP dispensation and accountability, reviewing daily dosing diaries, performing the Instillation Comfort Questionnaire, the Eyedrop Acceptability Questionnaire and all discussions with study subjects related to IMP.

11 COMPLIANCE WITH GOOD CLINICAL PRACTICES, ETHICAL CONSIDERATIONS, AND ADMINISTRATIVE ISSUES

This trial will be conducted in compliance with the protocol, Good Clinical Practices (GCPs), including the International Conference on Harmonization (ICH) Guidelines, and in general, consistent with the Declaration of Helsinki. In addition, all applicable local, state, and federal requirements relevant to the use of IMPs in the countries involved will be adhered to.

11.1 Protection of Human Subjects

11.1.1 Subject Informed Consent

Informed consent must take place before any trial specific procedures are initiated. Signed and dated written informed consent must be obtained from each subject prior to enrollment into the trial.

All informed consent forms must first be approved by the sponsor and receive approval from an IRB/IEC prior to their use. If the consent form requires revision (e.g., due to a protocol amendment or significant new safety information), it is the investigator's responsibility to ensure that the amended informed consent is reviewed and approved by the governing IRB/IEC and that it is read, signed and dated by all subjects subsequently enrolled in the trial as well as those currently enrolled in the trial, as recommended by the governing IRB.

11.1.2 Institutional Review Board (IRB) Approval

This trial is to be conducted in accordance with Institutional Review Board regulations (U.S. 21 CFR Part 56.103). Only an IRB/IEC approved version of the informed consent form will be used.

11.2 Ethical Conduct of the Trial

This trial will be conducted in accordance with the ethical principles that originated with the Declaration of Helsinki.

11.3 Subject Confidentiality

All personal trial subject data collected and processed for the purposes of this trial should be maintained by the investigator and his/her staff with adequate precautions as to ensure that the confidentiality of the data is in accordance with local, state, and federal laws and regulations.

Monitors, auditors and other authorized representatives of CRO, the sponsor, the IRB/IEC approving this trial, the FDA, the Department of Health and Human Services, other domestic government agencies, and other foreign regulatory agencies will be granted direct

access to the trial subject's original medical and trial records for verification of the data and/or clinical trial procedures. Access to this information will be permitted to the aforementioned individuals to the extent permitted by law.

A report of the results of this trial may be published or sent to the appropriate health authorities in any country in which the IMP may ultimately be marketed, but the subject's identity will not be disclosed in these documents.

11.4 Documentation

Source documents may include a subject's medical records, hospital charts, clinic charts, the investigator's trial subject files, as well as the results of diagnostic tests such as X-rays, laboratory tests, and EKGs. The investigator's electronic copy of the eCRFs serves as the investigator's record of a subject's trial-related data.

11.4.1 Retention of Documentation

All trial related correspondence, subject records, consent forms, record of the distribution and use of all IMP and copies of case report forms should be maintained on file for at least two years after the last approval of a marketing application in an ICH region and until there are no pending or contemplated marketing applications in an ICH region; or until at least two years have elapsed since the formal discontinuation of clinical development of the IMP. These documents will be retained for a longer period if required by the applicable regulatory requirements or by an agreement with the sponsor. It is the responsibility of the sponsor to inform the investigator/institution as to when these documents no longer need to be retained. The investigator must notify the sponsor prior to destroying trial documentation even after the above-mentioned time has passed.

If the responsible investigator retires, relocates, or for other reasons withdraws from the responsibility of keeping trial records, custody must be transferred to a person who will accept the responsibility. The sponsor must be notified in writing of the name and address of the new custodian.

11.5 Recording of Data on Source Documents and Electronic Case Reports Forms (eCRFs)

All subject data will be captured in the subject source documents which will be entered into the eCRFs in the Electronic Data Capturing System (EDC). The investigator is responsible for ensuring that trial data is completely and accurately recorded in the source documents, data entered into each subject's eCRF, and all trial-related materials. All trial data should also be attributable, legible, contemporaneous, and original. Recorded data should only be corrected in a manner that does not obliterate, destroy, or render illegible the previous entry (e.g., by drawing a single line through the incorrect entry and writing the revision next to the corrected data).

The EDC system is conforms to 21 CFR Part 11 requirements and data entry into the system will be performed only by staff that have been trained and have access to the system. An audit trail will be maintained within the system to capture all changes made within the database. After the end of the trial and database lock, copies of all applicable subjects' eCRFs will be provided to each investigator site to be maintained on file by the investigator.

11.6 Monitoring and Quality Assurance

During the course of the trial a clinical research associate (CRA) will make routine site visits to review protocol compliance, assess IMP accountability, and ensure the trial is being conducted according to the pertinent regulatory requirements. The review of the subjects' medical records will be performed in a manner that adequately maintains subject confidentiality. Further details of the trial monitoring (including medical monitoring) will be outlined in a monitoring plan.

Domestic and foreign regulatory authorities, and quality assurance, sponsor and or its designees may carry out on-site inspections and/or audits which may include source data checks. Therefore, direct access to the original source data will be required for inspections and/or audits. All inspections and audits will be carried out with consideration to data protection as well as subject confidentiality to the extent that local, state, and federal laws apply.

11.7 Handling of Biological Specimens

Not applicable.

11.8 Publications

Authorship and manuscript composition will reflect cooperation among all parties involved in the trial. Authorship will be established before writing the manuscript. The trial sponsor will have the final decision regarding authorship, manuscript and publication.

13 APPENDICES

Appendix 1 Schedule of Assessments (in recommended order)

Procedure	Visit 0 Within 14 days before Visit 1 (Day -14 to -1)	Visit 1 Day 1	Visit 2 Day 15 ± 1	Visit 3 Day 29 ± 2	Visit 4 /ET) Day 57 ± 2
Informed Consent / HIPAA	X				
Demographics	X				
Medical/Surgical History	X				
Previous/Concomitant Medication	X	X	X	X	X
Inclusion/Exclusion Criteria	X	X			
Urine Pregnancy Test	X	X			X
Dryness Score (VAS severity of dryness)*		X	X	X	X
VAS*		X	X	X	X
OSDI*	X	X	X	X	X
Eyedrop Acceptability Questionnaire*					X
Visual Acuity (ETDRS)	X	X	X	X	X
Slit-Lamp Biomicroscopy	X	X	X	X	X
TFBUT*	X	X			X
Corneal Fluorescein Staining (NEI scale)*	X	X	X	X	X
Meibomian Gland Assessment (MGD score)*	X	X			X
Schirmer's Test I (without anesthesia)*	X	X			X
Intraocular Pressure	X				X
Dilated Fundoscopy	X				X
Randomization (via IRS)		X			
In-office instillation of randomized IMP		X			
Instillation Comfort Questionnaire		X			
Adverse Event Query	X	X	X	X	X
Dosing Diary Dispensation and/or Review		X	X	X	X
Dispensation of trial medication		X	X	X	
Collection of trial medication			X	X	X
Trial Exit					X

*= Assessment to be conducted in the order as depicted in the Schedule of Assessments; ETDRS = Early Treatment of Diabetic Retinopathy Study; HIPAA = Health Information Portability and Accountability Act; NEI = National Eye Institute; OSDI = Ocular Surface Disease Index; TFBUT = Tear Film Break Up Time; ET= Early Termination; VAS: burning/stinging, sticky feeling, foreign body sensation, itching, blurred vision, sensitivity to light, pain, frequency of dryness, and awareness of dry eye symptoms

[figure not shown]
Appendix 2 Instructions for Administration of Eye Drops

Instructions for Use

Subjects will be instructed to instill one drop in each eye four times daily as illustrated below. Subjects will be instructed to use a second drop only if the first drop misses the eye. Subjects will be given detailed instructions on study drug administration (see below), accountability, and storage.

Note: On day of study Visits 2, 3 and 4, subjects should make sure that their dose of the study drug is instilled at least 2 hours before the start time of the visit.

Proper Handling of Eye drop Container

Note: Please contact study site staff immediately for replacement if you notice any damage with study drug container.

Figure A. Opening the bottle

1. Unscrew the cap of the bottle.
2. Prior to the first administration of the study drug you must separate the cap from the safety seal ring below the cap and remove it.
3. Do not touch the dropper after removing the cap.
4. To avoid loss of solution **please read steps 5 to 7** carefully before applying the eye drops.
5. Hold the opened bottle with the dropper pointing upwards and gently press the bottle between thumb and index finger.
6. Keep the bottle under slight pressure and turn the bottle until the dropper points downwards.
7. With the dropper pointing downwards reduce the pressure on the bottle to allow some air to flow into the bottle.

Figure B. Instilling the drop

[figure not shown]
1. Lean your head back slightly and carefully pull down your lower eyelid. Look upwards.
2. Hold the opened bottle with the dropper pointing downwards above your eye. Apply gentle pressure on the bottle and administer 1 drop per eye.

Note: Due to the special properties of the study drug you may not feel the drop falling into your eye. In this case we recommend application in front of a mirror.

3. Do not touch the dropper with your eye or lashes.
4. For an even distribution, close your eyes after applying the study drug.

5. Put the screw cap back on after administration.

If a subject has difficulties with step 4 to 7 of Figure A, advise to refer to step 2 of Figure B: subject to squeeze bottle very gently or to wait until drop drips from the bottle without squeezing.

[figure not shown]

[figure not shown]
[REDACTED]

[REDACTED]
[REDACTED]
[REDACTED]
[REDACTED]
[REDACTED]
[REDACTED]
[REDACTED]
[REDACTED]

[REDACTED]
[REDACTED]

[figure not shown]
[REDACTED]

[figure not shown]
The figure consists of 20 groups of horizontal bars. Each group contains 3 or 4 bars of varying lengths. The bars are black on a white background. The first 19 groups have 3 bars each, while the last group has 4 bars. The bars in each group are offset vertically.

A large black rectangular redaction box covers the majority of the page content, starting below the header and ending above the footer. The redaction is composed of several horizontal lines of varying lengths, with a few vertical lines and small black squares interspersed within the horizontal lines, creating a textured appearance. The redaction is positioned in the center of the page, leaving a white margin on all four sides.

[REDACTED]

The figure consists of two rows of 10 horizontal black bars each. The top row contains bars of varying lengths, with the longest bar in the center and shorter bars at the ends. The bottom row contains bars of varying lengths, with the first bar being very short and the last bar being very long, creating a visual effect of perspective or depth. The bars are black on a white background.

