6 TRIAL PARAMETERS

6.1 Efficacy Endpoints

6.1.1 Primary Efficacy Endpoints:

Two primary endpoints will be tested in the following order using hierarchical fixed sequence testing:

1. Change from baseline (CFB) in total Corneal Fluorescein Staining (tCFS) (NEI scale) at Day 57
2. CFB of Dryness Score (visual analogue scale [VAS] Severity of Dryness) at Day 57

6.1.2 Secondary Efficacy Endpoints:

The following secondary efficacy endpoints will be evaluated in the following order using hierarchical fixed sequence testing:

1. CFB of Dryness Score (VAS) at Day 15
2. CFB in total Corneal Fluorescein Staining (tCFS) (NEI scale) at Day 15
3. CFB of VAS burning/stinging at Day 57
4. CFB in central Corneal Fluorescein Staining (cCFS) (NEI scale) at Day 57

6.1.3 Other Pre-specified Efficacy Endpoints:

1. CFB of Dryness Score (VAS) at Day 29
2. CFB in tCFS at Day 29
3. CFB in CFS central and inferior sub-regions (NEI scale) to each measured post-baseline visit.
4. Proportion of tCFS responders (≥ 3 improvement based on NEI scale) at Day 57.
5. Proportion of Dryness Score responders ($\geq 30\%$ improvement from baseline) at Day 57.
6. CFB in VAS burning/stinging, sticky feeling, foreign body sensation, itching, blurred vision, sensitivity to light, pain, frequency of dryness, and awareness of dry eye symptoms at each measured post-baseline visit.
7. CFB in Ocular Surface Disease Index (OSDI[®]) at each measured post-baseline visit.

[REDACTED]

[REDACTED]
[REDACTED]
[REDACTED]

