7 TRIAL MATERIALS

7.1 Investigational Medicinal Product(s)

7.1.1 IMP(s)/ Formulation (s)

NOV03 drug product is a thin, clear, preservative-free ophthalmic solution drop (see [Table 1](#)). Saline eye drops preserved with benzalkonium chloride will be supplied as the control product (see [Table 2](#)). Investigational drug and control will be provided in identical bottles and labels to ensure the double-masked character of the trial.

Table 1 Active Investigational Product

	Investigational Product
Product code:	NOV03
Chemical name:	Perfluorohexyloctane
Molecular formula:	C ₁₄ H ₁₇ F ₁₃
Dosage form:	3 mL ophthalmic solution
Unit dose:	11 µL drop size; 100% perfluorohexyloctane
Route of administration:	Topical ocular administration
Physical description:	Colorless and clear ophthalmic solution
Excipients:	None

Table 2 Control Investigational Product

	Control Investigational Product
Product name:	Saline solution
Chemical name:	Sodium chloride solution (0.6 %)
Molecular formula:	NaCl
Dosage form:	3 mL ophthalmic solution
Unit dose:	35-40 µL drop size
Route of administration:	Topical ocular administration
Physical description:	Colorless and clear ophthalmic solution
Excipients:	0.01% benzalkonium chloride w/v

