7.4 IMP Masking

Investigational drug and control will be provided in identical bottles and labels to ensure the double-masked character of the trial. The Investigator/site staff and Bausch & Lomb, Incorporated. personnel or designee(s) involved in the conduct of the trial will be masked to the IMP. Clinical Trial Material Supply Chain are unmasked designee.

Due to physicochemical differences between NOV03 and saline, there will be a dedicated dosing coordinator who will be responsible for the handling of IMP and activities (such as dispensation, collection, accountability) surrounding the use of IMP.

Each site must have a dedicated dosing coordinator that will be responsible for:

- all IMP dispensation and accountability,
- daily diary dosing education/review,
- all discussions with study subjects related to IMP,
- the administration of the Eyedrop Acceptability and Instillation Comfort Questionnaires.

This designee shall not participate in any other trial procedures and not report this information to other staff. Subjects will be instructed to administer the IMP out of the sight of the Investigator or site staff other than the dedicated dosing coordinator. Subjects are not to show or discuss the properties of the assigned IMP to the Investigator or site staff other than the dedicated dosing coordinator, unless instructed to do so.

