8.5 Compliance with Protocol

Subjects will be instructed on proper instillation and storage of IMP at Visits 1, 2, and 3, and provided with written instructions (see Appendix 2). The used and unused IMP bottles will be collected from subjects at Visits 2, 3 and 4 to assess subject dosing compliance.

Subject dosing compliance will be determined by the subject’s response or lack thereof to the prompt “Was the dose taken?” in the subject diary. If more than 20% of the responses to the total expected dose-taken prompts are checked “no,” left blank, or missing, then the subject will be deemed noncompliant for dosing and a deviation recorded e.g., 12 checked “no,” left blank, or missing at Visit 2 and Visit 3 and more than 24 at Visit 4.

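### The subject instruction sheet attributes an unfelt drop to the study drug's properties, an avoidable masking cue when subjects rate the second primary endpoint

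*Protocol*

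**What the plan says.** Protocol Appendix 2 gives subjects step-by-step instructions for instilling the drops. A note beside the instillation step reads "Due to the special properties of the study drug you may not feel the drop falling into your eye", and goes on to suggest using a mirror when that happens. Sections 7.1.5 and 8.5 refer to Appendix 2 for subjects generally, and neither describes separate sheets for the two arms.

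Section 7.1.1 describes two different products. NOV03 is listed with "11 µL drop size; 100% perfluorohexyloctane" and no excipients. The control is listed with "35-40 µL drop size" and contains benzalkonium chloride. Section 7.4 acknowledges the consequence: "Due to physicochemical differences between NOV03 and saline, there will be a dedicated dosing coordinator" who handles all product-related contact with subjects.

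Section 9.4 says that subjects are to be masked. Section 6.1.1 makes "CFB of Dryness Score (visual analogue scale [VAS] Severity of Dryness) at Day 57" the second of two primary endpoints, tested after total corneal fluorescein staining (tCFS).

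**The concern.** A difference in feel between the two drops is built into the products, and the plan cannot remove it. What the plan can control is whether subjects are told how to interpret it. The note links not feeling the drop to a special quality of the study drug. A subject who never feels the drop may take that as a sign of the active product, and one who always feels it may take that as a sign of the control. The comparison can be repeated at each of four daily doses over the treatment period.

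This matters because the subject is the rater. The Dryness Score at Day 57 is a confirmatory claim in its own right and the gateway to every secondary test (Section 10.4.4). Two of the four secondary endpoints, Dryness at Day 15 and burning/stinging at Day 57, are also subject-rated VAS scores. If subjects who believe they are on active treatment report more improvement, and those who believe they are on control report less, the shift goes straight into the estimated treatment difference. A larger sample would not remove it.

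**Working it through.** **1. Does each link hold in the documents?**

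- *Same text for both arms.* Yes, as far as the visible text shows: one sheet, with no arm-specific version.
- *Sensation may differ by arm.* Plausible. The volume ratio is 35/11 = 3.2 to 40/11 = 3.6, and Section 7.4 concedes physicochemical differences. The documents do not report how often either drop is felt.
- *Safeguards against a subject's own inference.* None visible. Identical bottles and labels (Sections 7.1.1, 7.4) hide appearance, not feel. The dosing coordinator and out-of-sight dosing (Section 7.4) keep information from the investigator and site staff. The rule against discussing the product with other participants (Sections 4.3, 10.6) limits comparison between subjects. It does not stop a subject comparing a sensation with the sheet.
- *Check on masking.* No visible section plans a treatment-guess question, a blinding index or a related sensitivity analysis. Parts of the endpoint sections and Appendix 3 are redacted, so one cannot be ruled out.

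**2. The plan's own power figure**

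Inputs from Section 10.3: 250 per arm, difference 10, SD 28, two-sided alpha 0.05.

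- SE = 28 × √(2/250) = 2.504
- Power = Φ(10/2.504 − 1.96) = 97.9%, as stated
- The tCFS inputs (1.0 and 2.8) have the same ratio and also give 97.9%; jointly 0.979 × 0.979 = 95.8%, as stated
- Smallest significant Dryness difference = 1.96 × 2.504 = 4.9 points

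**3. How sensitive is the Dryness test to a small reporting bias?**

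Suppose there is no true Dryness effect and a differential reporting bias of b points in favour of NOV03. The chance of a false superiority finding is Φ(b/SE − 1.96).

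| b (points) | SD 28 (planning value) | SD 26 (NVU-002, synopsis) |
|---|---|---|
| 0 | 2.5% | 2.5% |
| 1 | 5.9% | 6.3% |
| 2 | 12.3% | 13.6% |

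These are for the Dryness test taken alone. It is reached only if tCFS is significant first.

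**4. What would produce a bias of that size?**

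The documents give no guess rate and no shift per guess, so this step is assumption throughout. If the same shares guess in each arm and a guess moves the score by a fixed amount in the expected direction:

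b = 2 × (share guessing right − share guessing wrong) × shift

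- 20% right, none wrong, shift of 5 points: 2 × 0.20 × 5 = 2 points
- 20% right, 10% wrong, shift of 5 points: 2 × 0.10 × 5 = 1 point

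Wrong guesses cancel right ones. The formula also covers guessing from any cue. It does not isolate the part that comes from the sentence.

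**The case against.** The sentence does not single out the active arm. Throughout Appendix 2 the term study drug means whatever is in the subject's own bottle, so a saline subject can read the note as being about saline. It is hedged, and it never says that feeling the drop means control. Each subject is assigned only one product, so nobody is set to compare an 11 µL drop with a 35-40 µL one, and nothing visible says subjects are told the volumes. The note also has a use: subjects may take a second drop only if the first misses, and someone who feels nothing could wrongly conclude that it missed.

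All of this stands. It limits how much the sentence can reveal and explains why the advice should stay in some form. It does not explain why the advice needs its causal clause, because the mirror suggestion works without it.

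A reader might infer that the sentence unmasks the trial, or that a bias of several points on the Dryness Score can be attributed to it. The documents support neither. They contain no guess data, and part of any guessing would come from the product difference, which rewording leaves in place. Nor is the Dryness Score a co-primary on which trial success depends: Section 10.2 declares success on tCFS alone, which staff who are meant to be masked assess.

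**Conclusion.** The point holds in a narrow form. The causal clause in Appendix 2 is an avoidable masking cue, given to subjects who rate a confirmatory endpoint, and no visible safeguard addresses a subject's own inference from it. It is a cheap improvement to make, not an error in the analysis or the sample size; the stated power reproduces.

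The size of any bias from this sentence is unknown and could be close to zero. The rise from 2.5% to about 6-12% shows only how little differential reporting (1 to 2 points, against a planned effect of 10) the Dryness test can absorb. It assumes no true Dryness effect, SD 28, 250 per arm and a bias entirely in favour of NOV03.

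**What to change.** In the Appendix 2 note, delete the opening clause that attributes the lack of sensation to the study drug's properties. Replace the note with neutral text that keeps its purpose, such as: *You may or may not feel the drop. If unsure, apply it in front of a mirror.* Ask the dosing coordinator to use the same neutral wording when instructing subjects verbally under Section 7.1.5.

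The cost is IRB handling of one revised sentence of subject material. Product, dose, procedures, analysis and sample size do not change. The edit removes the hint but not the sensory difference, so it lowers the risk without eliminating it.
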